4. LIST OF ABBREVIATIONS AND DEFINITIONS OF TERMS

The following abbreviations and terms are used in this study protocol.

Table 2:Abbreviations and Terms

Abbreviation or	E should be
Term	Explanation
λ _z	apparent terminal-phase elimination rate constant
ADA	antidrug antibody
ADCC	antibody-dependent cell-mediated cytotoxicity
AE	adverse event
ALT	alanine aminotransferase
AST	aspartate aminotransferase
aHUS	atypical hemolytic uremic syndrome
AUC_{∞}	area under the serum concentration versus time curve from zero to infinity
AUCt	area under the serum concentration versus time curve from time zero to the last quantifiable concentration
BMI	body mass index
BP	British Pharmacopoeia
C5b-9	terminal complement complex
CAP	complement alternative pathway
CBC	complete blood count
CDC	complement-dependent cytotoxicity
CH50	50% hemolytic complement activity (screening test for deficiency of classical complement
	pathway in which hemolysis of liposomes sensitized by specific antibodies is measured; one
	CH50 unit is the volume or dilution of serum that lyses 50% of liposomes)
CL	total body clearance of drug from the serum
C _{max}	maximum observed serum concentration
cRBC	chicken red blood cell
CRU	clinical research unit
CTCAE	Common Terminology Criteria for Adverse Events
CV	coefficient of variation
ECG	electrocardiogram
eCRF	electronic case report form
EOI	end of infusion
GCP	Good Clinical Practice
HBcAb	hepatitis B core antibody
HBsAg	hepatitis B surface antigen
HBV	hepatitis B virus
HCV	hepatitis C virus
HIV	human immunodeficiency virus
IB	Investigator's Brochure
ICF	informed consent form
ICH	International Council for Harmonisation
IEC	independent ethics committee
IRB	institutional review board
IV	intravenous(ly)
mAb	monoclonal antibody
MAD	multiple ascending dose
MAD MCV4	1 0
	tetravalent meningococcal conjugate vaccine
OP DD	outpatient
PD	pharmacodynamic(s)

Ph Eur	European Pharmacopoeia
РК	pharmacokinetic(s)
PNH	paroxysmal nocturnal hemoglobinuria
Q4W	every 4 week
QTcF	QT interval corrected using the Fridericia's formula
RBC	red blood cell(s)
SAD	single ascending dose
SAE	serious adverse event
SBA	serum bactericidal antibody
SC	subcutaneous(ly)
SOI	start of infusion/injection
SOM	study operations manual
SRC	Safety Review Committee
$t_{1/2}$	terminal elimination half-life
TB	tuberculosis
T _{max}	time to maximum observed serum concentration
ULN	upper limit of normal
V _d	volume of distribution
WBC	white blood cell(s)

5. INTRODUCTION

ALXN1210 is a humanized monoclonal antibody (mAb) that is structurally related to eculizumab (Soliris[®]) and is being developed by Alexion Pharmaceuticals, Inc. (Alexion). It specifically binds to the human complement protein C5, inhibiting its cleavage to C5a and C5b during complement activation. This inhibition prevents the release of the proinflammatory mediator C5a and inhibits the formation of the cytolytic pore-forming membrane attack complex (MAC) terminal complement complex (C5b-9) while preserving the proximal or early components of complement activation (eg, C3 and C3b) essential for the opsonization of microorganisms and clearance of immune complexes. The mechanism of action provides a rationale for the potential therapeutic use of ALXN1210 in diseases where complement activation is involved (eg, paroxysmal nocturnal hemoglobinuria [PNH], atypical hemolytic uremic syndrome [aHUS]). These disorders of uncontrolled complement activation (PNH and aHUS) are chronic and progressive with severe morbidities and significant premature mortality (Hillmen, 1995; Kavanagh, 2006).

5.1. Background

Detailed information about the known and expected benefits, risks, and reasonably anticipated adverse events (AEs) of ALXN1210 may be found in the current edition of the Investigator's Brochure (IB).

5.1.1. Clinical Studies

ALXN1210 has been administered safely to healthy subjects in 200 mg and 400 mg intravenous (IV) doses in a single ascending dose (SAD) study (Study ALXN1210-HV-101, N = 10). Healthy subjects have also been administered multiple 400 mg and 800 mg IV doses on an every 4 week (Q4W) regimen in an ongoing multiple ascending dose (MAD) study (Study ALXN1210-HV-102, N = 12). The starting doses of ALXN1210 IV in these 2 healthy volunteer studies were selected to assess safety in healthy volunteers and to have measurable pharmacologic activity (eg, inhibition of complement activation) based on the therapeutic exposure required with eculizumab. No safety concerns have been identified in either of the Phase 1 studies, both of which were randomized, blinded, and placebo controlled. In the completed Study ALXN1210-HV-101 (SAD), no serious adverse drug reactions, treatment discontinuations, or deaths were reported.

Conclusions from Study ALXN1210-HV-101 are as follows:

- ALXN1210 exhibited prolonged pharmacokinetic (PK) exposure with mean geometric half-life estimates of 32.4 days and 30.8 days following single doses of 200 and 400 mg, respectively.
- The PK parameters (area under the serum concentration versus time curve from time zero to the last quantifiable concentration $[AUC_t]$, area under the curve from time zero to infinity $[AUC_{\infty}]$, and maximum observed serum concentration $[C_{max}]$) increased in a slightly less than dose-proportional manner over the studied range of 200 to 400 mg based on the protocol-specified statistical analysis.

- Following single 200 mg and 400 mg doses of ALXN1210 IV, all 6
 pharmacodynamic (PD) variables (total complement C5 serum concentration, free
 complement C5 serum concentration, chicken red blood cell [cRBC] hemolysis,
 classical complement pathway [CCP] activity, complement alternative pathway
 [CAP] activity, and plasma C5b-9 activity) showed dose-dependent reductions from
 baseline. The effect of ALXN1210 on these PD variables was immediately evident
 after end of infusion (EOI). At the EOI, the mean free C5 serum concentrations and
 cRBC hemolysis activity were inhibited by > 99% and > 97%, respectively.
- The duration of the effect was longer following a 400-mg dose than a 200-mg dose.
- All subjects were negative for antidrug antibody (ADA) through Day 150.

In addition, multiple doses of ALXN1210 IV have been administered to patients with PNH.

5.1.2. Nonclinical Studies

The binding characteristics, potency, and effector functions of ALXN1210 have been studied in vitro and compared with its parent molecule, eculizumab. ALXN1210 does not bind with strong affinity to any FcyR subclass or to C1q, and has shown only a modest increased binding capacity to FcyRIIa relative to eculizumab. Based on the structure of the antibody (IgG4 FcR portion) and the soluble target, ALXN1210 is unlikely to be capable of initiating antibody-dependent cell-mediated cytotoxicity (ADCC) or complement-dependent cytotoxicity (CDC) in vivo. In Study ALXN1210-HV-101, no indication of CDC or ADCC was observed.

ALXN1210 does not exhibit pharmacologic activity or cross-reactivity with any nonhuman animal species (including cynomolgus monkey), prohibiting the design of a predictive nonclinical safety testing strategy. Because ALXN1210 is specific for human C5, nonclinical safety tests (safety pharmacology, general toxicity, and reproductive toxicology) will not be predictive of human on-target toxicity. Moreover, significant immunoreactivity (ADA) to ALXN1210 was observed in a non-GLP PK study in cynomolgus monkeys. In the animals with a positive ADA response, clearance of ALXN1210 was accelerated. This observation suggests that interpretation of results from nonhuman primate toxicology studies performed with ALXN1210 (evaluating only potential off-target effects), might be further confounded by an antibody response, and consequent effects on test article clearance.

To study the potential toxicity of long-term inhibition of C5 and to evaluate the influence of such inhibition on reproductive function, a 26-week repeat-dose toxicity study in mice and Segment I, II, and III reproduction studies in mice were performed using a surrogate murine anti-mouse C5 mAb (BB5.1). Like ALXN1210, the BB5.1 surrogate antibody binds directly to and prevents the cleavage of C5, thereby inhibiting the generation of both C5a and C5b-9 in the mouse. These studies showed no meaningful adverse observations at doses that blocked C5 in a sustained fashion.

In addition to the studies with a surrogate antibody, GLP tissue cross-reactivity studies were performed using a standard set of human and cynomolgus monkey tissues. These studies confirmed the lack of cross-reactivity in a nonhuman primate and demonstrated no unexpected binding to human tissues.

An attempt was made to study the potential local irritation in rabbits of ALXN1210, when administered subcutaneously (SC) with a previous formulation; however, the results were not interpretable due to the development of a severe immune-complex based immunologic response. Such immune responses in animals are not considered predictive of similar potential outcomes in humans. To assess the potential for immunogenicity with ALXN1210, the amino acid substitutions to eculizumab used to make ALXN1210 were modeled in the context of the binding motifs for MHC class II receptors using the Immune Epitope Database Analysis Resource (IEDB, 2016; http://tools.iedb.org/main/). None of the peptide fragments in ALXN1210 that are novel relative to eculizumab were predicted to confer high affinity binding to MHC class II receptors.

5.1.3. General Considerations for This Study

This Phase 1 study will be performed in healthy subjects. Data from this study will be used to evaluate the safety, immunogenicity, PK, and PD investigations obtained in subjects receiving a single dose of ALXN1210 SC compared to results obtained in subjects receiving a single dose of ALXN1210 IV.

5.1.4. Potential Risks

5.1.4.1. Infections (*Neisseria meningitidis* and Other Encapsulated Organisms)

A risk associated with complete terminal complement inhibition, such as that anticipated with ALXN1210, is infection with encapsulated organisms, particularly *N meningitidis*. Clinically, this risk is mitigated in patients receiving complement inhibitors such as eculizumab by vaccinating all patients against *N meningitidis* with a tetravalent meningococcal conjugate vaccine (MCV4) before dosing.

In the current setting, ie, normal healthy subjects with an induced transient state of complement deficiency, subjects will receive the MCV4 vaccination at least 56 days prior to dosing with ALXN1210 (if not vaccinated with MCV4 within the last 3 years, or if adequate documentation to verify previous vaccination is unavailable). The serum bactericidal antibody (SBA) titer to the tetravalent vaccine will be established prior to enrollment. Subjects who are not already vaccinated will also receive vaccination for serotype B meningococcal infections at least 56 days prior to Day 1 dosing with a booster administered at least 28 days prior to dosing on Day 1.

In addition to vaccination against *N meningitidis* with MCV4 and the serogroup B vaccine, all subjects will be treated with prophylactic antibiotics (oral penicillin V 500 mg twice daily) for the duration of reduced complement activity, ie, until complement activity is predicted to be restored to normal based on an exposure-response analysis of data from clinical study ALXN1210-HV-101. Unless the investigator and sponsor agree to an alternative regimen, all subjects will take prophylactic antibiotics (oral penicillin V 500 mg twice daily) until complement activity has normalized (anticipated at Day 56).

Analysis of serum samples to establish actual complement activity will be performed using a CH50 in vitro liposome immunoassay (LIA). The analysis will take place approximately when complement activity is expected to normalize. Results will be used to confirm that complement activity has returned to normal and, once confirmed prophylactic antibiotic treatment can be stopped. All subjects will be closely monitored for signs of infection throughout the study.

5.1.4.2. Immunogenicity and Hypersensitivity

Treatment with any therapeutic protein (human, humanized, chimeric) may induce an immune response. Occasionally, this immune response is clinically significant. The consequences of an immune reaction to a therapeutic protein range from transient appearance of antibodies without any clinical consequence, to severe, life-threatening conditions. Potential clinical consequences also may include the following: severe hypersensitivity-type reactions; decrease in efficacy; and induction of autoimmunity, including antibodies to the endogenous form of the protein (Casadevall, 2002; Li, 2001).

Some patients treated with IV infusions of mAbs have experienced concurrent infusion-related reactions with signs or symptoms that can be classified as acute allergic/hypersensitivity reactions or cytokine release syndrome (Bugelski, 2009; Castells, 2015). The signs and symptoms include headache, fever, facial flushing, pruritus, myalgia, nausea, chest tightness, dyspnea, vomiting, erythema, abdominal discomfort, diaphoresis, chills, hypertension, lightheadedness, hypotension, palpitations, and somnolence. Anaphylaxis might occur at any time during an infusion. In addition, readministration of some mAbs has been associated with serum sickness-like reactions, manifesting 1 to 14 days after study drug administration.

6. STUDY OBJECTIVES AND PURPOSE

The purpose of the study is to evaluate the safety, tolerability, pharmacokinetics (PK), pharmacodynamics (PD), and immunogenicity of a single dose of ALXN1210 administered subcutaneously (SC) compared to a single dose of ALXN1210 administered intravenously (IV) in healthy subjects. Data from this study will be used to determine the absolute bioavailability of ALXN1210 SC in healthy subjects.

6.1. **Primary Objectives**

The primary objectives of this study are as follows:

- To evaluate the safety and tolerability of a single dose of ALXN1210 SC compared to ALXN1210 IV in healthy subjects, as assessed by physical examination findings, vital sign measurements, immunogenicity, laboratory analysis, and assessments of AEs.
- To determine the absolute bioavailability of ALXN1210 SC.

6.2. Secondary Objectives

The secondary objective of the study is as follows:

• To evaluate the PD effects of ALXN1210 SC compared to ALXN1210 IV, as assessed by the level of free C5 and chicken red blood cell (cRBC) hemolysis.

7. ENDPOINTS

The safety, immunogenicity, PK, and PD endpoints are described in the sections to follow. The timing of assessments is displayed in the Schedule of Assessments (Section 9).

7.1. Safety Endpoints

Safety endpoints include the following:

- Change from baseline in physical examination findings
- Change from baseline in vital sign measurements
- Incidence of ADA measured via immunogenicity testing
- Change from baseline in electrocardiogram (ECG) parameters
- Change from baseline in laboratory measurements
- Incidence of AEs and serious AEs (SAEs)

7.2. Pharmacokinetic Endpoints

The following PK parameters will be evaluated:

- Maximum observed serum concentration (C_{max})
- Time to maximum observed serum concentration (T_{max})
- Area under the serum concentration versus time curve from time zero to the last quantifiable concentration (AUC_t)
- Area under the serum concentration versus time curve from time zero to infinity (AUC_{∞})
- Terminal elimination rate constant (λ_z)
- Terminal elimination half-life $(T_{\frac{1}{2}})$
- Total body clearance of drug from the serum (CL)
- Volume of distribution (V_d)

7.3. Pharmacodynamic Endpoints

The following PD effects will be evaluated:

- Change in serum total and free C5 concentrations over time
- Change in cRBC hemolysis over time

8. INVESTIGATIONAL PLAN

[figure not shown]
8.1. Overall Study Design

This is a Phase 1 study designed to evaluate the safety, tolerability, PK, PD, and immunogenicity of a single 400 mg dose of ALXN1210 SC compared to a single 400-mg dose of ALXN1210 IV or placebo SC in 42 healthy subjects. All subjects will be screened for eligibility in the study after providing signed and dated institutional ethics committee-approved written informed consent to participate and before any study specific screening procedures are performed.

Subjects who fail to meet eligibility criteria may not be rescreened for participation in the study, unless the condition that led to eligibility failure is transient, self-limited, and easily treatable, and is expected to be resolved at the time of dosing, as agreed by the investigator and medical monitor.

Six subjects will initially be randomly assigned in a 2:1 ratio to Cohort 1a, in a blinded fashion, to receive either a single 400-mg dose of ALXN1210 SC or single dose of placebo SC (Figure 1). The Safety Review Committee (SRC) will evaluate the first 48 hours of post-dose clinical safety data for subjects in Cohort 1a before enrollment into Cohorts 1b or 2 may begin. Thirty-six subjects will then be randomly assigned, in a 2:1 ratio, to either Cohort 1b (N=24) or Cohort 2 (N=12). Within Cohort 1b, the 24 subjects will further be randomly assigned, in a 5:1 ratio and blinded fashion, to receive either a single 400-mg dose of ALXN1210 SC or a single dose of placebo SC, respectively. The 12 subjects in Cohort 2 will receive a single 400 mg dose of ALXN1210 IV in an open-label fashion.

Figure 1: Study Diagram

Abbreviations: A = active drug; IV = intravenous; P = placebo; SC = subcutaneous; SRC = Safety Review Committee Note: The SRC will review the first 48 hours of post-dose safety data from Cohort 1a before enrollment into Cohorts 1b or 2 may begin.

At the sponsor's discretion, up to 8 additional subjects (2 subjects each in Cohorts 1a and 1b and 4 subjects in Cohort 2) may be enrolled into the study if 2 or more subjects discontinue within 3 months for reasons other than drug-related AEs, and after consultation with the SRC. All enrolled subjects will be included in analyses as appropriate. Subjects in Cohorts 1a and 1b will be combined for analyses. Subjects who withdraw from the study subsequent to dosing will be followed for safety assessments through the last scheduled study visit, if possible.

Subjects will participate in the study for up to 39 weeks, including a screening period of up to 70 days, followed by a 200-day follow-up period for safety, PK, PD, and immunogenicity assessments after study drug administration.

8.2. Number of Subjects

Forty-two subjects are planned for evaluation of the primary and secondary objectives in this study: 6 (4 ALXN1210 SC, 2 placebo SC) subjects in Cohort 1a; 24 (20 ALXN1210 SC, 4 placebo SC) subjects in Cohort 1b, and 12 (ALXN1210 IV) subjects in Cohort 2. At the sponsor's discretion, up to 8 additional subjects (2 subjects each in Cohorts 1a and 1b and 4 subjects in Cohort 2) may be enrolled into the study if 2 or more subjects discontinue within 3 months for reasons other than drug-related AEs, and after consultation with the SRC.

8.3. Dose Rationale

8.3.1. ALXN1210 IV Dose

The geometric mean (coefficient of variation [CV]) ALXN1210 half-life in Study ALXN1210-HV-101 ranged from 30.8 (10.2%) to 32.4 (16.2%) days over the studied doses. Following single 200-mg and 400-mg doses of ALXN1210 IV to healthy volunteers, all studied PD variables showed dose-dependent changes from baseline that recovered back to baseline. The effect of ALXN1210 on these PD variables was immediately evident after EOI. At the EOI, the mean free C5 serum concentrations and cRBC hemolysis activity were inhibited by > 99% and > 97%, respectively. In the ongoing Study ALXN1210-HV-102, 400-mg and 800-mg (Q4W) doses of ALXN1210 IV are being studied to assess safety, tolerability, PK, PD, and immunogenicity in healthy volunteers.

8.3.2. ALXN1210 SC Dose

A single dose of 400 mg, equivalent to 4 mL, will be administered SC via 4 x 1 mL injections in the abdominal area. Administration of a single 400-mg dose of ALXN1210 SC is expected to have an acceptable safety profile. Single doses of 400 mg of ALXN1210 SC and placebo SC, administered as described in this protocol, are anticipated to provide data from which multiple dose simulations may be generated in order to project the dosing regimens necessary to achieve therapeutic serum concentrations (> 50 μ g/mL) in patients.

8.4. Dose Continuation and Suspension/Stopping Rules

Parallel randomization of 36 subjects into Cohort 1b and Cohort 2 will occur based on review by the SRC of the first 48 hours of post-dose clinical safety data from the 6 subjects in Cohort 1a. Enrollment into Cohort 1b and Cohort 2 will proceed as described in Table 3. These rules apply to AEs assessed as related to study drug by the investigator.

Group toxicity rules:

- Toxicity refers to clinically significant drug-related adverse reaction(s).
- 'Cohort progression' refers to progression to a consecutive dose/dosing regimen in line with the dose progression rules and minimum data requirements.
- 'Suspension' refers to no further IMP being administered at the dose level/dosing regimen concerned and that further cohort progression will be suspended. If a dosing regimen is suspended, an ad hoc SRC meeting will be held. Any resumption at the same dose level/dosing regimen will require a substantial amendment, which has been approved by the competent authority and the IEC.

CTCAE Grade	Severity/ Seriousness	Number of Subjects Affected	Action	Effect on cohort progression		
Ι	Mild	N/A ≤ 2 subjects in different SOC	Dose regimen may continue.	Study continues as per clinical study protocol.		
Π		2 subjects in same SOC OR 3 subjects in different SOC	Dose regimen may continue.	Cohorts 1b and 2 may commence, if they have not already.		
	Moderate	 ≥ 3 subjects in same SOC OR ≥ 4 subjects in different SOC 	All dose regimens suspended UNLESS the toxicity is either a local tolerability event or and injection/infusion site reaction, in which case only the affected cohort is suspended.	Study continuation (if both cohorts stopped) requires substantial amendment. Continuation of the affected cohort (for local tolerability or injection/infusion site reactions) requires substantial amendment.		
III		1 subject	Dose regimen may continue.	Cohorts 1b and 2 may commence, if they have not already.		
	Severe	≥ 2 subjects	All dose regimens suspended UNLESS the toxicity is either a local tolerability event or and injection/infusion site reaction, in which case only the affected cohort is suspended.	Study continuation (if both cohorts stopped) requires substantial amendment. Continuation of the affected cohort (for local tolerability or injection/infusion site reactions) requires substantial amendment.		
IV V	Life- threatening Fatal	\geq 1 subject	Study suspended.	Study continuation requires substantial amendment.		
SAE	Serious	≥ 1 subject	Study suspended.	Study continuation requires substantial amendment.		

Abbreviations: CTCAE = Common Terminology Criteria for Adverse Events; SAE = serious adverse event; SOC = system organ class.

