8.5. Safety Review Committee

The SRC is composed of the medical monitor, clinical scientist, biostatistician, pharmacovigilance representative, clinical pharmacologist, and investigator. The membership, schedule of meetings, data required for each safety review, and requirements for documenting meeting discussions and outcome will be outlined in the SRC charter.

In order to perform its primary function of ensuring subject safety, the members of the SRC will have access to all safety and clinical data.

The SRC will review the first 48 hours of post-dose clinical safety data for the 6 subjects randomly assigned into Cohort 1a before enrollment into Cohorts 1b or 2 may begin. This will allow for further assessment of safety and tolerability of the SC formulation before exposing additional subjects to ALXN1210 SC. After the SRC has reviewed the safety and clinical data of the last completed subject in Cohort 1a, subjects will be randomly assigned into Cohort 1b in a blinded fashion, to receive either a single 400-mg dose of ALXN1210 SC or a single dose of placebo. In parallel, subjects will be randomly assigned into Cohort 2 to receive a single 400-mg dose of ALXN1210 IV in an open-label fashion.

The SRC will convene to review safety data if unexpected safety concerns arise. The SRC will conduct a review of the clinical and safety data of individual subjects if prespecified criteria as described in Table 3 are met that warrant suspension of the study.

The SRC may make recommendations regarding safety issues, study conduct, and modifying (ie, exploring the dose cohort further, suspending dose cohort[s]), or stopping the study.

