8.6. Criteria for Study Termination

The investigator, competent authority, or sponsor may terminate the study for reasonable cause. Conditions that warrant termination of the study include, but are not limited to, the following:

- Discovery of an unexpected, serious, or unacceptable risk to subjects enrolled in the study
- Decision on the part of the sponsor to suspend or discontinue testing, evaluation, or development of the study drug
- Failure of the investigator to comply with the approved protocol, pertinent guidelines, and/or regulations
- Submission of knowingly false information from the investigator to the sponsor and/or regulatory authorities

The end of the study will be defined as the date of the last subject's last visit.

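### Read row by row, Protocol Table 3 suspends dosing for three Grade II subjects in one SOC, but not when one of the three is a non-serious Grade III

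*Protocol*

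**What the plan says.** Protocol Section 8.4 limits the rules to events that the investigator judges related to study drug. Table 3 then works grade by grade:

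- **Grade II, continue:** "2 subjects in same SOC OR 3 subjects in different SOC".
- **Grade II, suspend:** "≥ 3 subjects in same SOC OR ≥ 4 subjects in different SOC". All regimens stop, unless the toxicity is a local tolerability event or a site reaction, "in which case only the affected cohort is suspended".
- **Grade III:** one subject allows the regimen to go on, with the same progression text as the Grade II continue row ("Cohorts 1b and 2 may commence, if they have not already"). Two or more subjects suspend, on the same terms as Grade II.
- **Grade IV or V, or any related SAE:** one subject suspends the study, and "Study continuation requires substantial amendment".

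Suspension "refers to no further IMP being administered at the dose level/dosing regimen concerned". It also triggers an ad hoc SRC meeting, and resuming needs a substantial amendment approved by the competent authority and the ethics committee.

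The rows are labelled II and III. Neither Section 8.4 nor Section 8.5 says how to treat a mixture of the two grades.

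Outside the table, Section 8.5 states: "The SRC will convene to review safety data if unexpected safety concerns arise". Section 8.6 states: "The investigator, competent authority, or sponsor may terminate the study for reasonable cause".

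**The concern.** A stopping rule should not become less strict because one subject's event is worse. If the grades are counted separately, moving one of three subjects from Grade II to Grade III takes that subject out of the Grade II count. It adds only one to the Grade III count, which suspends at two. Section 16.3 describes Grade 3 as incapacitating, so the rule would be easing in the wrong direction.

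The stake is the automatic part of the safeguard: the mandatory halt, the SRC meeting that follows it, and the amendment needed before dosing can resume. It matters while dosing is under way. Of the 42 planned healthy subjects, 36 are dosed after the SRC's review of Cohort 1a. Section 12.6 caps dosing at 6 subjects a day, so the rule has to work over at least 36 / 6 = 6 further dosing days.

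**Working it through.** **Inputs.** The thresholds come from Table 3. The check takes one related, non-serious event per subject. Let g2 and g3 be the numbers of subjects with Grade II and Grade III events.

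**Rule as written, row by row.** Suspend if g3 ≥ 2, or if g2 within one SOC ≥ 3, or if the different-SOC count at Grade II ≥ 4. That last count has two possible readings: (A) the number of SOCs with a Grade II event, or (B) the total number of Grade II subjects.

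| Pattern | Grade II row sees | Grade III row sees | Result |
|---|---|---|---|
| 3 Grade II, one SOC | 3 in same SOC | 0 | suspend |
| 2 Grade II + 1 Grade III, one SOC | 2 in same SOC | 1 | continue |
| 1 Grade II + 2 Grade III, one SOC | 1 | 2 | suspend |
| 4 Grade II, four SOCs | 4 in different SOCs | 0 | suspend |
| 3 Grade II + 1 Grade III, four SOCs | 3 in different SOCs | 1 | continue |

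The second and fifth rows are the reversals. Both hold under readings A and B.

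**How far it extends.** Enumerating every pattern of 1 to 6 subjects over SOCs gives 2 + 6 + 14 + 33 + 70 + 149 = 274 patterns. Changing a single Grade II to Grade III can lift a suspension from 8 starting patterns under A and 5 under B. All of them start with no Grade III event, because a second Grade III suspends by itself. Three are common to both readings:

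- 3 in one SOC: changing any of the 3 lifts the suspension.
- 3 in one SOC plus 1 elsewhere: only the 3 same-SOC events lift it.
- 1 in each of four SOCs: changing any of the 4 lifts it.

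**With cumulative counting.** Replace g2 by g2 + g3 in the two Grade II conditions. Comparing the two rules with g2 and g3 each from 0 to 7, the one-SOC result changes only at (g2, g3) = (2, 1), and the different-SOC result only at (3, 1). In the 274 patterns, reversals fall to 0 under both readings.

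**Price in extra suspensions.** The documents give no event rates by SOC, so these are assumptions. Take N = 42 and per-subject probabilities p2 and p3. Suspend if g3 ≥ 2 or the count reaches T. The two rules differ only when g2 = T − 1 and g3 = 1, so the increase is

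N! / [(T−1)! · 1! · (N−T)!] × p2^(T−1) × p3 × (1−p2−p3)^(N−T).

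At p2 = 5% and p3 = 1%:

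- T = 4 (four-subject count alone): 447,720 × 0.05³ × 0.01 × 0.94³⁸ = 0.053. The chance of suspension goes from 21.4% to 26.7%.
- T = 3 (all events in one SOC): 34,440 × 0.05² × 0.01 × 0.94³⁹ = 0.077. The chance goes from 39.6% to 47.3%.

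Over p2 of 3%, 5%, 8% and 10% and p3 of 0.5%, 1% and 2%, the increase runs from 1.6 points (T = 4, 3% and 0.5%) to 10.2 points (T = 3, 5% and 2%). These figures count events at any time in the study, so they overstate the effect on dosing. They do not model the local-reaction exception or several events in one subject.

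**The case against.** **The grades may not be meant as exclusive.** Table 3 does not say that a Grade III subject drops out of the Grade II count, any more than it says that such a subject stays in. An SRC could count cumulatively. This stands, and it is why the point is tied to the row-by-row reading. It does not remove the problem: a stopping rule should state its counting convention, and if cumulative counting is intended, the fix only writes it down.

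**Nothing compels dosing.** A reader might infer that Table 3 obliges the trial to keep dosing after a severe reaction, or leaves subjects unprotected. The documents do not support that. The continue rows are permissive, the SRC sees all safety data and may recommend suspension (Section 8.5), urgent safety measures apply (Section 21.4), and the study can be terminated (Section 8.6). These powers limit the harm. They rest on judgment, whereas the table makes the stop automatic for the milder pattern.

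**The gap is narrow.** Under Section 16.2, important medical events and persistent or significant disability or incapacity are serious, so some Grade III events would suspend the study as SAEs. The same section separates severity from seriousness, so non-serious Grade III events remain possible. Section 16.6 records a worsened event on a new line, so its Grade II line may still count; the gap is clearest for events that are Grade III from onset. From the 2 + 1 pattern, one more Grade II in that SOC, or a second Grade III in any SOC, suspends. All of this stands.

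**The pattern counts can mislead.** The 8 or 5 starting patterns might be taken as that many defects, or as a frequency. They are neither: they are unweighted variants of the same counting gap.

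**The SRC charter is not available.** It may schedule further reviews, but Section 8.4 does not refer to it for how grades are counted.

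**Conclusion.** The point holds in conditional form and is worth considering. On a row-by-row reading, Table 3 gives a less strict result for worse toxicity in two basic cases: 2 Grade II + 1 Grade III in one SOC, and 3 Grade II + 1 Grade III across four SOCs. The result rests on three conditions: each subject is counted at one grade, the Grade III event is related but non-serious, and dosing is still in progress. The size of the defect is a missing automatic trigger, not a missing ability to stop. No probability of occurrence is claimed, because the percentages in the working rest on assumed rates.

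**What to change.** Change only the Grade II suspension cell, to: *≥ 3 subjects with a related event of Grade II or higher in same SOC OR ≥ 4 such subjects in different SOC*. Equivalently, add a footnote that Grade III subjects also count toward the Grade II thresholds. Either way, state that each subject counts once per SOC at the worst grade, and that the strictest applicable row governs. Leave every threshold, the Grade III, IV/V and SAE rows, and the exception for local reactions as they are.

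The cost is one protocol amendment. It needs ethics committee approval before implementation (Section 21.1) and, if classed as substantial, competent-authority approval as well. No data or visits are added. Somewhat more suspensions would follow, within the range shown in the working, and each would need a substantial amendment before dosing at that regimen could resume.
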